## 5.4. Study Patients

### 5.4.1. Analysis Population

Table JGDN.5.2 lists analysis population definitions and associated data type for analysis.

**Table JGDN.5.2. Analysis Populations**

Population	Definition	Analysis Type / Variable	Note
All Entered Patients	All patients who signed Inform Consent		
Safety Population	All entered patients who received any quantity of study drug	Baseline characteristics, concomitant medication, efficacy analyses, Safety, e.g. dosing/exposure, AE and resource utilization.	For efficacy analysis, patients will be grouped according to the assigned dose level cohort.
DLT-evaluable Population	Patients who complete Cycle 1 (Part A/B Cycle 2 for combination treatment) or discontinue due to a DLT prior to completing Cycle 1 treatment (Part A/B Cycle 2 for combination treatment)	DLT assessment/AE	For safety analysis, patients will be grouped according to the actual dose level received.

Abbreviations: AE = adverse event; DLT = Dose-Limiting Toxicity.

#### **5.4.2. Patient Disposition**

A detailed description of patient disposition will include:

- Summary of the number of patients who entered into the study, and who received at least one dose of study treatment, by site, dose level, overall.
- The summary of the number (and percent) of patients with the primary reasons for discontinuation from study treatment and patients still receiving treatment by dose level and overall. The discontinuation reasons collected in CRF (eg. AE, PD, death, and etc) will be presented.
- Listing of patient discontinuation.

#### **5.4.3. Demographic and Baseline Characteristics**

The following patient demographic and other baseline characteristics will be summarized:

- patient demographics: age (years) and age group, gender, race (White, Black, Asian, All Other), ethnicity, height (cm), weight (kg), and BSA (m^2), Karnofsky and Lansky performance status
- baseline disease characteristics:
  - at study entry only: current disease stage, grade, duration of disease (months)

- prior cancer therapies: type of therapy (surgery, radiotherapy, systemic therapy), type of prior surgery, type of prior radiotherapy, and type of prior systemic therapy
- Medical history by MedDRA PT, presented in decreasing frequency

Note: Subjects reporting more than 1 condition/diagnosis within a PT will be counted only once for that PT.

Patient listings of demographic data and baseline characteristics will be provided. Patient listings of prior cancer therapies (surgery, radiotherapy, and systemic therapy) will also be provided.

Other patient characteristics will be summarized as deemed appropriate.

## 5.5. Important Protocol Deviations

Protocol deviations will be identified in Protocol Deviation Plan. Important protocol deviations (e.g. not meeting inclusion/exclusion criteria, noncompliance with protocol procedures, dosing errors, use of prohibited medication, continuing after meeting withdrawal criteria) will be listed by treatment group and by category of deviations.

## 5.6. Concomitant Medications

The following concomitant medications used during study treatment period or up to the 30-day postdiscontinuation follow-up period will be summarized by numbers and percentages by dose cohort, presented in decreasing frequency of the World Health Organisation drug term:

- all concomitant medications
- premedication for study drug

Patient listing of all concomitant therapies and premedications will be provided.

## 5.7. Treatment Compliance

The number of dose omissions, reductions, and delays, and the number of cycles received will be summarized by cohort.

A by-patient listing of treatment compliance data will be provided.

## 5.8. Efficacy Analyses

The study was not designed to make an efficacy assessment. Exploratory efficacy analysis will be performed to investigate antitumor activity within each combination arm. The efficacy analysis will include all treated patients (ie. Safety Population). Tumor response data will be tabulated according to dose cohort and combination arm. A listing of best overall response will be provided by cohort. Best overall response will be summarized by dose cohort and combination arm. The objective response rate (ORR=CR+PR) and disease control rate (DCR=CR+PR+SD) along with the 90% exact confidence interval (CI) will be tabulated for each cohort and combination arm. For patients having CR/PR, the median duration of response,

together with a 90% CI will be estimated using Kaplan-Meier method. The median PFS will be estimated along with 90% CI by dose cohort and combination arm, using Kaplan-Meier method.

Any deaths observed during the study will be summarized descriptively and possibly interpreted in the context of study drug dose for each patient observed to have died. Dependent on the maturity of the data, overall survival may be analyzed using time-to-event methods, such as Kaplan-Meier.

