Vincristine: will be administered intravenously. Vincristine (patients \geq 10 kg: 1.5 mg/m², patients <10 kg: 0.05mg/kg. Dose is capped at 2 mg) is to be administered on Day 1 and Day 8 of each 21-day cycle.

Irinotecan: will be administered intravenously. Irinotecan (50 mg/m²) is to be administered on Days 1, 2, 3, 4, and 5 of each 21-day cycle.

Ifosfamide: will be administered intravenously. Ifosfamide (2.8 g/m²) is to be administered on Days 1, 2, 3, 4, and 5 of each 21-day cycle, for up to 6 cycles or a cumulative dose of 84 g/m².

Mesna: commercial formulations will be used and administered intravenously. Mesna should be administered at a minimum dose equal to 60% of the ifosfamide dose according to institutional guidelines.

Planned Duration of Treatment:

The planned duration of treatment is not fixed; patients will remain on study until they fulfill one of the criteria for study discontinuation.

Follow-up in post-treatment discontinuation: 30 days (\pm 7 days) for patients with disease progression. For patients who have discontinued study treatment due to toxicity or reasons other than progressive disease, follow-up will continue every 6 weeks (\pm 7 days) until progression.

Criteria for Evaluation:

Efficacy:

Radiographic assessments will be performed at baseline and then every 2 cycles (\pm 7 days) until radiographic documentation of progressive disease. Response Evaluation Criteria In Solid Tumors, Version 1.1 criteria should be used for all solid tumors with the exception of central nervous system tumors. Response Assessment in Neuro-Oncology Criteria or Macdonald Criteria should be used for central nervous system tumors.

Safety: The safety and tolerability of the study treatment is determined by reported adverse events (AEs), physical exam including vital signs, clinical laboratory tests, electrocardiograms, and results of echocardiogram / multigated acquisition scans. Adverse events will be coded using the Medical Dictionary for Regulatory Activities (MedDRA®) and graded using National Cancer Institute Common Terminology Criteria for Adverse Events (NCI-CTCAE) Version 4.0 and summarized by System Organ Class and preferred term.

Pharmacokinetic/Pharmacodynamic:

Blood samples will be collected at various time points for PK assessment for olaratumab levels and the levels of the combination chemotherapies. Blood samples will be collected at various time points for immunogenicity analysis.

Tailoring Genetics and Biomarkers:

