- The patient has radiographic progressive disease or significant symptomatic disease deterioration characterized as progression of disease, in the opinion of investigator, in the absence of radiographic evidence of progressive disease.
- The patient experiences unacceptable toxicity (for example, a persistent moderate toxicity that is intolerable to the patient).
- The patient is noncompliant with study procedures and/or treatment (Section 7.6).

The reason for and date of discontinuation will be collected for all patients. The date of discontinuation (for any of the above reasons) from study treatment is to be reported on the electronic case report form (eCRF). Patients who discontinue will have follow-up procedures performed as shown in the Study Schedule ([Attachment 1](#)).

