8.1.2.1. Serious Adverse Events

Serious adverse event collection begins after the patient has signed informed consent and has received study drug. If a patient experiences an SAE after signing informed consent, but prior to receiving study drug, the event will not be reported as serious unless the investigator feels the event may have been caused by a protocol procedure.

Planned surgeries should not be reported as SAEs unless the underlying medical condition has worsened during the course of the study.

Planned hospitalizations or elective procedures for underlying preexisting conditions that are already recorded in the patient's medical history at the time of study enrollment should not be considered SAEs. Hospitalization or prolongation of hospitalization without a precipitating clinical AE (for example, for the administration of study therapy or other protocol-required procedure) should not be considered SAEs.

An SAE is any adverse event during this study that results in one of the following outcomes:

- death
- initial or prolonged inpatient hospitalization (except for study drug administration)
- a life-threatening experience (that is, immediate risk of dying)
- persistent or significant disability/incapacity
- congenital anomaly/birth defect
- considered significant by the investigator for any other reason

Important medical events that may not result in death, be life-threatening, or require hospitalization may be considered SAEs when, based on appropriate medical judgment, they may jeopardize the patient and may require medical or surgical intervention to prevent one of the outcomes listed in this definition.

Serious adverse events due to disease progression, including death, should not be reported unless the investigator deems them to be possibly related to the study drug.

Study site personnel must alert Lilly or its designee of any SAE within 24 hours of investigator awareness of the event via a sponsor-approved method. If alerts are issued via telephone, they are to be immediately followed with official notification on study-specific SAE forms. This

24-hour notification requirement refers to the initial SAE information and all follow-up SAE information.

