8.1.2.2.3. Follow-Up Visit

All AEs and SAEs, regardless of relatedness to study drug(s) or protocol procedures, occurring during the follow-up visit (Visit 801) must be reported to Lilly or its designee. The follow-up visit (Visit 801) starts one day after the decision is made to discontinue the patient from the study. At the end of the follow-up visit, the patient will be required to have specific safety assessments ([Attachment 1](#)). The timing of these safety assessments is 30 days \pm 7 days after the decision is made to discontinue the patient from the study.

Following the safety assessments, which mark the end of the follow-up visit (Visit 801), the patient will be discontinued from the study, unless there is an ongoing AE or SAE that is possibly related to study drug. In this instance, the patient should be followed in subsequent long-term follow-up visits until the event is resolved, the event is no longer considered to be drug-related, the event becomes stable or returns to baseline, a new treatment is initiated for the patient, or the patient dies or is lost to follow-up.

If it is deemed to be in the best interest of the patient to start a new anticancer treatment prior to the scheduled end of the follow-up visit, the follow-up visit duration may be shortened. In this case, the follow-up assessments should be completed prior to the initiation of the new therapy.

After the follow-up visit (Visit 801), AEs are not required to be reported unless the investigator feels the AEs were related to either study drug, drug delivery system, or a protocol procedure. If an investigator becomes aware of an SAE believed to be related to protocol procedures or study drug, the investigator should report the SAE to the sponsor, and the SAE will be entered in the Lilly Safety System.

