Imaging Studies (CT/MRI)	X (if applicable)	X	For patients who have discontinued study treatment due to toxicity or reasons other than progressive disease, imaging studies and tumor assessments are to be obtained every 6 weeks (± 7 days) until progression or initiation of other anticancer therapy. RECIST v1.1 should be used for all tumors with the exception of CNS tumors; RANO or Macdonald criteria should be used for CNS tumors.
RECIST v1.1, RANO, or Macdonald Tumor Assessments	X (if applicable)	X	
Subsequent Anti-Cancer Treatments, and Associated Disease Progression Date		X	For all patients, details on subsequent anticancer treatment (start/stop dates and treatments administered) and first post-study treatment disease progression date should be recorded.
Other Assessments			
PK Sampling	X		See Attachment 4 for details.
Biomarker Sampling	X		

Abbreviations: AE = adverse event; CNS = central nervous system; CRF = case report form; CT = computed tomography; ECG = electrocardiogram; ECHO = echocardiogram; IRR = infusion-related reaction; MRI = magnetic resonance imaging; MUGA = multi-gated acquisition; PK = pharmacokinetics; RANO = Response Assessment in Neuro-Oncology; RECIST = Response Evaluation Criteria In Solid Tumors.

- a **Short-term follow-up** begins the day after the patient and the investigator agree that the patient will no longer continue study treatment and lasts approximately 30 days (± 7 days). The date of this agreement is to be reported on the CRF as the date of discontinuation from study treatment.
- b **Long-term follow-up** begins the day after short-term follow-up is completed. Patients that discontinue study treatment for reasons other than progression will be followed every 6 weeks (± 7 days) until progression.

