**Table JGDN.5.1. Censoring Rule of PFS Primary Analysis**

Situation	Event / Censor	Date of Event or Censor
Tumor progression or death	Event	Earliest date of PD or death
No tumor progression and no death	Censored	Date of last adequate radiological assessment or date of first study dose
unless		
No baseline radiological tumor assessment available	Censored	Date of first study dose
No adequate postbaseline radiological tumor assessment available and death reported after 2 scan intervals following first study dose	Censored	Date of first study dose
New anticancer treatment started and no tumor progression or death within 14 days	Censored	Date of adequate radiological assessment prior to (start of new therapy +14 days) or date of first study dose (whichever is later)
Tumor progression or death documented immediately after 2 or more consecutive missing scan intervals following last adequate radiological tumor assessment or first study dose (whichever is later)	Censored	Date of last adequate radiological assessment prior to the missing assessment or date of first study dose

Abbreviations: CR = complete response; PD = progressive disease; PFS = progression free survival; PR = partial response; SD = stable disease.

- a Symptomatic deteriorations (that is, symptomatic progressions, which are not radiologically confirmed) will not be considered as disease progressions.
- b Adequate radiological tumor assessment refers to an assessment with one of the following responses: CR, PR, SD, or PD.
- c The 2-scan interval is counted from the date of last adequate tumor assessment to the date of next 2 scheduled tumor assessments plus 14 days (adjusted by tumor assessment window).
- d Refer to flow chart in [Appendix 1](#) if a patient meets multiple censoring criteria.
- e If there are multiple dates associated with 1 assessment, the assessment date will be set to the first date when the overall response is PD and the last date otherwise.

**Overall survival (OS)** is defined as the time from the date of first study dose to death due to any cause. Patients will be censored at the date of last known alive.

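### SAP 5.8 permits a Kaplan-Meier overall survival analysis, but the protocol plans no survival follow-up after progression, so censoring is likely informative and would generally overstate survival

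*SAP*

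**What the plan says.** **Analysis.** SAP 5.8 first plans a descriptive summary of deaths observed during the study and then adds: "Dependent on the maturity of the data, overall survival may be analyzed using time-to-event methods, such as Kaplan-Meier". Maturity is not defined. SAP 5.3.2 measures OS from first dose to death from any cause, with this rule: "Patients will be censored at the date of last known alive".

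**Follow-up.** Progression ends treatment. The discontinuation criteria in Protocol 6.3.1 include: "The patient has radiographic progressive disease or significant symptomatic disease deterioration characterized as progression of disease". For patients with progression the Synopsis gives "Follow-up in post-treatment discontinuation: 30 days", with a window of 7 days either way. Protocol 8.1.2.2.3 continues: "Following the safety assessments, which mark the end of the follow-up visit (Visit 801), the patient will be discontinued from the study". The one exception there is an ongoing adverse event possibly related to study drug. Long-term follow-up is defined in footnote b of the follow-up table in Attachment 1: "Patients that discontinue study treatment for reasons other than progression will be followed every 6 weeks". It stops at progression.

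**Other routes to later information.** One row in the long-term column of that table reads: "For all patients, details on subsequent anticancer treatment (start/stop dates and treatments administered) and first post-study treatment disease progression date should be recorded". For deaths, Protocol 8.1.2.1 says: "Serious adverse events due to disease progression, including death, should not be reported unless the investigator deems them to be possibly related" to study drug.

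**Status of OS.** Protocol 5.2.2 names PFS and ORR under antitumor activity, not OS. SAP 5.8 calls the efficacy analysis exploratory and says the study was not designed to assess efficacy.

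**The concern.** Kaplan-Meier estimates survival correctly only if patients censored at a given time have the same later risk of death as those still observed. Here a patient leaves observation because the disease has progressed. In relapsed or refractory solid tumors the risk of death would ordinarily be expected to be higher after progression than before. The curve then rests mainly on patients who have not progressed.

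Waiting does not cure this. More calendar time adds deaths among patients still progression-free, but few deaths among those who progressed and left. A data set can look mature while most deaths remain unseen.

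What is at stake is the reading of an exploratory curve. Protocol 5.3 reports adult median OS of 26.5 and 14.7 months, so a pediatric OS curve would invite comparison, although the documents plan none. No dose decision rests on OS.

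**Working it through.** The documents give no OS event target, expected pediatric survival or maturity threshold, so there is no planned figure to reproduce. The check has two parts.

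**1. Who is observed, and until when**

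- Stopped for progression: one visit at about 30 days, then off study (Synopsis; Protocol 8.1.2.2.3).
- Stopped for another reason: every 6 weeks, until progression (Attachment 1, footnote b).
- No schedule contains a survival visit or a vital-status item.
- After the 30-day visit, only serious events believed related to study drug or procedures are reportable, so a later death from disease has no planned route into the database.

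**2. Size under stated assumptions**

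Assumed, because the documents are silent: exponential PFS with hazard λ; a share q of PFS events that are deaths; exponential post-progression survival with hazard μ; discontinuation on the day of progression; last contact 30 days later, w = 30/30.4375 = 0.986 months (month length from SAP 5.3).

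True survival: S(t) = e^(−λt) + (1−q)·λ·(e^(−λt) − e^(−μt))/(μ−λ).

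Recently progressed patients still under observation, per progression-free patient: r = (1−q)·λ·(1 − e^(−(μ−λ)w))/(μ−λ). During the first 30 days, replace w by t. If λ = μ, take the limits.

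Hazard that Kaplan-Meier sees: h = (qλ + μr)/(1 + r).

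This h is a weighted mean of the death hazard before progression (qλ) and after it (μ). The true hazard is the same mean with all surviving progressed patients counted, so it gives μ more weight. Kaplan-Meier therefore overstates survival when μ > qλ, is unbiased when they are equal, and understates it when μ < qλ.

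*Worked case, medians 3 and 6 months.* λ = 0.693/3 = 0.2310 and μ = 0.693/6 = 0.1155. With q = 0, r = 0.2310 × 1.044 = 0.241 and h = 0.1155 × 0.241/1.241 = 0.0224 per month. Over 12 months the cumulative hazard is about 0.0224 × 11.014, plus about half that rate over the first 0.986 months, which is 0.258. Kaplan-Meier survival is e^(−0.258) = 77%. True survival is 0.0625 + 0.375 = 43.75%.

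- q = 10%: h = (0.0231 + 0.1155 × 0.217)/1.217 = 0.0396; Kaplan-Meier 63%, true 0.0625 + 0.3375 = 40%.
- q = 20%: h = (0.0462 + 0.1155 × 0.193)/1.193 = 0.0574; Kaplan-Meier 50.5%, true 0.0625 + 0.30 = 36.25%.

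*Grid.* Median time to progression 2, 3, 4 months by median post-progression survival 4, 6, 8 months, survival at 12 months. The share of deaths observed is q + (1−q)(1 − e^(−μw)).

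| Share of PFS events that are deaths | Kaplan-Meier | True | Deaths observed |
|---|---|---|---|
| 0% | 58-86% | 23-58% | 8-16% |
| 10% | 44-73% | 21-54% | 17-24% |
| 20% | 33-61% | 19-49% | 27-33% |

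Kaplan-Meier is above the truth in all 27 cells. The gap runs from about 4 points (medians 2 and 8, q = 20%: 41.5% against 37.6%) to about 37 points (medians 3 and 4, q = 0: 68.4% against 31.25%).

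*Sensitivity.* A wider simulated grid (PFS medians 1.4-4 months, post-progression medians 2-9 months, 48 cells) gave ratios of Kaplan-Meier to true median from 0.9 to 3.8. One cell was reversed and in one the median was not reached. Calibrated to the adult control arm in Protocol 5.3 (median PFS 4.1, OS 14.7 months), 12-month Kaplan-Meier survival was 87%, 75% and 64% for q = 0, 10 and 20%, against a true 60%, 59% and 58%. That is a calibration, not a pediatric expectation.

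**The case against.** **The size cannot be read from the documents.** A reader might infer that survival would be strongly overstated. That holds mainly if nobody dies without first progressing. PFS in SAP 5.3.2 counts death from any cause, and Protocol 6.1.1 admits performance scores down to 50, so some deaths before progression are plausible. Each such death shrinks the bias. This objection stands: direction can be argued, as likely; a single magnitude cannot.

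**Inflated medians would often not appear.** Arms have about 20 patients (Protocol 6.2). In the worked case with q = 0, the expected number at risk at 12 months is 20 × 0.0625 × 1.241 = 1.6. With q = 10%, simulated arms of 20 showed about 3 to 5 deaths and reached the median in roughly 35 to 51% of trials. This also stands, which is why size is given as 12-month survival.

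**Contact may not end at 30 days.** The row asking about subsequent therapy covers all patients, and an ongoing possibly related event extends follow-up. Either could move the last-known-alive date later, so an absolute cut at 30 days is too strong a reading. But the row has no visit schedule and no vital-status item, and it conflicts with footnote b and with Protocol 8.3, which asks for these data only from patients who stopped for reasons other than progression. Later contact for some patients does not make censoring independent.

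**The analysis is optional.** With few deaths, a statistician might judge the data immature and not run it. That is possible, but without a definition of maturity it is not a safeguard.

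**Conclusion.** The point holds as a conditional one. If the OS analysis in SAP 5.8 is run on data collected as the protocol plans, censoring is triggered by progression, is likely informative and would generally overstate survival. On the assumed grid, 12-month survival is overstated by about 4 to 37 percentage points, depending mostly on the share of PFS events that are deaths. This rests on exponential times, on assumed medians and shares, on last contact 30 days after progression, and on a death hazard that rises after progression. With equal hazards the bias is zero, and if the hazard fell it would reverse.

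A reader might also infer that the sponsor is committed to this analysis, or that the trial's conclusions depend on it. Neither follows: the analysis is optional and exploratory, and OS is not an objective.

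**What to change.** Delete the time-to-event OS sentence from SAP 5.8, and the OS definition with its censoring rule from SAP 5.3.2. Keep the descriptive death reporting in full: deaths observed during the study (SAP 5.8), and both all deaths and deaths within 30 days of last dose (SAP 5.9.2). Death reporting should not be narrowed to the 30-day window.

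The cost is small: one optional exploratory analysis is lost, and PFS, ORR and DCR are untouched.

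If the sponsor wants OS, the alternative is vital-status follow-up of every patient to a common cut-off date, with maturity defined in advance. That needs a protocol amendment and continued contact after progression. In either case, reconcile the all-patients row in Attachment 1 with footnote b and Protocol 8.3, so that the end of contact is clear.
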